Using the lower (more conservative) of the two effect sizes from our previous psilocybin and salvinorin A studies ($d = 0.89$), and an alpha of 0.05, 6 volunteers would be sufficient to detect effects on ratings of drug intensity with 95% power. Empirical and simulation studies have provided recommendations for sample size of imaging experiments (Zandbelt et al., 2008). For similar parameters, including an effect size of 0.89, alpha of 0.05, and 80% power, 21 participants are necessary to power an ROI-based analysis of effects on brain activity similar to behavioral effects of psilocybin. Far fewer participants would be necessary to detect effects similar to the behavioral effects of salvinorin A, though no specific sample size recommendations were made by Zandbelt and colleagues for such a large effect size ($\eta^2 = 0.81$, equivalent to $d > 4$). Thus, the proposed study of 20 participants would be powered to detect clinically significant differences in brain activity between placebo and salvinorin A conditions. Given that consent will be obtained at the initial in-person screening interview, we are requesting approval to consent up to a total of 200 volunteers.

MRI data analyses: MRI data will be preprocessed using standard methods. The time course of brain regions in standard brain atlases (e.g. Chen Atlas or Power Atlas) will be extracted and submitted to functional connectivity analysis.

Statistical analysis of behavioral data: Baseline demographic data will be summarized with descriptive statistics to describe the volunteer population. For measures assessed at multiple time-points, including subjective effects ratings, both time-course and peak-effect data will be examined. For outcomes assessed at screening and one week after the final salvinorin A session, a paired t-test will be used to assess change from baseline (screening). Behavioral measures (including monitor ratings, subjective effects ratings, and questionnaire data) will be correlated with brain-imaging outcome measures to investigate the relationship between individual differences in subjective drug response and individual differences in neural drug response.

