First experimental session day: During the first drug administration session day, similar to our previous research with salvinorin A (Johnson et al., 2011; Johnson et al., 2016; MacLean et al., 2013), participants will be administered salvinorin A via inhalation while lying down. At least one staff member will be present in the room to directly monitor the participant for at least 45 minutes after each drug administration. Staff members will rate participant behavior and ask the participant to make verbal ratings of subjective effects at set time intervals throughout the drug administration session. In our previous research with salvinorin A, subjective effects resolved within 45 minutes (Johnson et al., 2011; Johnson et al., 2016; MacLean et al., 2013). Volunteers will complete several questionnaires and computer-based assessments approximately 45 minutes after each drug administration.

Study staff will record observations of subject movement during the acute effects of salvinorin A. Participants who are particularly sensitive to the effects of salvinorin A may exhibit involuntary movement of head, torso, or appendages, or resting or kinetic tremor. If a given participant exhibits gross involuntary movement or resting tremor after drug administration during the first experimental session, the study team will determine if this movement would invalidate MRI data collection. If the volunteer exhibits involuntary movement that would invalidate MRI data collection, or reports no memory for the experience, the session may be repeated with a 12 µg/kg dose of salvinorin A. Study volunteers will not advance to the MRI experimental session if it is determined that they have exhibited involuntary movement judged likely to invalidate MRI data collection at both 15 and 12 µg/kg.

Schedule of Events for First Experimental Session Day

Time Point (minutes from drug administration)	Procedure	Description
-30 (or more)	Intake procedures	Participant will complete drug and pregnancy urine tests, and complete a pre-session questionnaire to assess the psychological “set” of the volunteer
-10 (approximate)	Setup	The participant will be brought to the experimental session room, and the prepared salvinorin A dose for this participant will be brought to the session room from the BPRU pharmacy. All materials and equipment for drug delivery and study monitoring will be set up.
0	Drug administration	Participant will be administered salvinorin A via inhalation while lying down.

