1	Post drug-administration measurement	Participant will rate overall drug strength. Monitors will rate observed intensity of drug effect and amount of spontaneous speech and movement of the participant.
2	Post drug-administration measurement	Participant will rate overall drug strength. Monitors will rate observed intensity of drug effect and amount of spontaneous speech and movement of the participant.

3	Post drug-administration measurement	Participant will rate overall drug strength. Monitors will rate observed intensity of drug effect and amount of spontaneous speech and movement of the participant.
4	Post drug-administration measurement	Participant will rate overall drug strength. Monitors will rate observed intensity of drug effect and amount of spontaneous speech and movement of the participant.
5	Post drug-administration measurement	Participant will rate overall drug strength. Monitors will rate observed intensity of drug effect and amount of spontaneous speech and movement of the participant.
10	Post drug-administration measurement	Participant will rate overall drug strength. Monitors will rate observed intensity of drug effect and amount of spontaneous speech and movement of the participant.
15	Post drug-administration measurement	Participant will rate overall drug strength. Monitors will rate observed intensity of drug effect and amount of spontaneous speech and movement of the participant. Monitors will also complete the Fahn-Tolosa-Marin Tremor Rating Scale.
20	Post drug-administration measurement	Participant will rate overall drug strength. Monitors will rate observed intensity of drug effect and amount of spontaneous speech and movement of the participant.
25	Post drug-administration measurement	Participant will rate overall drug strength. Monitors will rate observed intensity of drug effect and amount of spontaneous speech and movement of the participant.
30	Post drug-administration measurement	Participant will rate overall drug strength. Monitors will rate observed intensity of drug effect and amount of spontaneous speech and movement of the participant. Monitors will also complete the Fahn-Tolosa-Marin Tremor Rating Scale.

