45	Final questionnaires	Participant will rate overall drug strength and complete questionnaires describing the subjective effects experienced during the acute effects of salvinorin A. Monitors will rate observed intensity of drug effect and amount of spontaneous speech and movement of the participant. Monitors will also complete a questionnaire to rate the overall qualitative nature of the participant's session.

The schedule of events for the first experimental session day is approximate, but the listed events will always occur in the same sequence.

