Inhalation device: The inhalation delivery system (i.e. pipe) is made of glass. The part of the glass pipe which will hold the salvinorin A will be a 5 ml round bottom chemistry flask meeting American Society for Testing and Materials (ASTM) specification E438 for Type I, Class A borosilicate glass. The non-ferromagnetic tubing attached to the inhalation delivery system will be polytetrafluoroethylene (PFTE) tubing, which meets FDA standard for food contact, has a high maximum working temperature (260° C, which is higher than the 244-245° C vaporization point of salvinorin A), and does not thermally degrade until temperatures greater than 400° C. The tubing will be 0.635 cm inner diameter, and up to 400 cm in length. The same tubing will be used for a given subject or a set of new tubing will be used between drug administrations. Tubing will not be cleaned with solvents.

A label will be prepared for each test dose and affixed to the neck of the 5mL round bottom flask containing the dose. This label will be removed immediately prior to heating the flask for drug administration. Each dose will be labeled with subject name, date, session number, pharmacy compounding number, dose of salvinorin A, and a statement that the drug is limited to investigational use only.

Study Statistics

Primary outcome variable: The primary outcome measures for this study will consist of changes in activity and connectivity of brain regions during the acute effects of salvinorin A, compared to the preceding period after inhalation of the placebo condition (inhaled air).

Secondary outcome measures: The secondary outcome measures will include a range of subjective measures described below.

Subject-rated overall drug strength: Volunteers will be prompted to verbally rate the overall drug strength on an 11-point scale (0 – none, no effect to 10 – extreme, strongest imaginable) at various

time points (e.g., 1, 2, 3, 4, 5, 10, 15, 20, 25, 30, and 45 minutes after each drug inhalation) during the first experimental drug session day.

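### As listed, the first-session schedule exposes the monitors' intensity score to the volunteer's spoken drug-strength rating, so its planned correlation with imaging may partly repeat the self-report correlation.

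*Combined protocol and SAP*

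**What the plan says.** The Schedule of Events for First Experimental Session Day has rows at 1, 2, 3, 4, 5, 10, 15, 20, 25 and 30 minutes, each opening "Participant will rate overall drug strength. Monitors will rate observed intensity of drug effect" and going on to have monitors rate speech and movement as well. The 45-minute row also puts the volunteer's rating before the monitors' rating. The closing note calls the timings approximate but adds that "the listed events will always occur in the same sequence".

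The self-rating is oral. Under Secondary outcome measures, "Volunteers will be prompted to verbally rate the overall drug strength on an 11-point scale".

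The narrative headed First experimental session day mentions the two tasks the other way round and gives both to the same group: "Staff members will rate participant behavior and ask the participant to make verbal ratings of subjective effects at set time intervals". On staffing it says "At least one staff member will be present in the room to directly monitor the participant". No separate rater is described, nor any masking of monitors to the spoken answer, nor any rule that they write their score down first.

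On use of the data, the section Statistical analysis of behavioral data says: "Behavioral measures (including monitor ratings, subjective effects ratings, and questionnaire data) will be correlated with brain-imaging outcome measures". The stated aim is to relate individual differences in subjective response to individual differences in neural response.

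**The concern.** A score given by an observer is worth collecting beside a self-report to the extent that it carries information the self-report does not. If the observer has just heard the volunteer say a number, the score may drift toward that number. A brain measure that tracks self-report would then tend to track the monitor score as well, and a reader who sees two correlations could take the second as support for the first.

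The first session, as described, has no placebo inhalation, so the self-ratings are given in an open drug session. An observer score that did not lean on those ratings would be useful there. Once the scores are collected, influence of this kind cannot be separated from genuine agreement.

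**Working it through.** **1. What the texts fix.** The documents state no figure on this point, so the first check is a reading of the sections side by side.

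- Order within a time point: the schedule lists self-rating then monitor rating at 11 of 11 post-dose time points. The narrative mentions behaviour rating then self-rating. The note on sequence can be read as governing the rows only; it does not say that it fixes the two steps inside a row. The order is therefore listed but not expressly prescribed.
- Opportunity to hear the number: the self-rating is spoken and asked for by the staff who also rate behaviour.
- Items exposed: mainly observed intensity, which lies closest to the volunteer's drug-strength scale. Amount of speech and movement is less exposed. The tremor scale, at 15 and 30 minutes, has its own observation procedure and is not part of this point.
- Route into the analysis: monitor ratings are named among the measures to be correlated with imaging. The Schedule of Events for Second Experimental Session Day lists no monitor ratings. The scheduled monitor scores thus come from the first session and the imaging from the second.

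**2. What the size could be.** The documents give no monitor-self correlation, no scale for the monitor intensity score and no expected brain-behaviour correlation. The following is an illustration on assumed inputs only.

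Assumptions: self-rating p and an uninfluenced monitor score m, both standardised, with corr(m, p) = 0.5. The recorded score is (1 − w)m + wp, where w is the fraction by which monitors move toward the spoken number. A brain measure has correlation 0.6 with p and no link to m except through p.

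corr(recorded, p) = [0.5(1 − w) + w] / √[(1 − w)² + w² + w(1 − w)]

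corr(brain, recorded) = 0.6 × corr(recorded, p)

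| w | corr(recorded, p) | shared variance | corr(brain, recorded) |
|---|---|---|---|
| 0 | 0.50 | 25% | 0.6 × 0.50 = 0.30 |
| 0.2 | 0.60/√0.84 = 0.65 | 43% | 0.39 |
| 0.3 | 0.65/√0.79 = 0.73 | 53% | 0.44 |
| 0.5 | 0.75/√0.75 = 0.87 | 75% | 0.52 |

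**3. What that means at the planned 20 completers.** Two-sided 5% significance needs |r| of about 0.444: with 18 degrees of freedom t = 2.101, and 2.101/√(18 + 2.101²) = 0.444. The expected values at w = 0.2 and 0.3 fall short of this, the second only just; the value at w = 0.5 exceeds it. By Fisher's z (standard error 1/√17), the chance of a significant brain-monitor correlation is about 25% at w = 0, 40% at w = 0.2 and 66% at w = 0.5.

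**4. How far a change of order helps.** If monitors record first at every time point, they no longer hear the current number before scoring. They have still heard an earlier one at 10 of the 11 time points, all but the 1-minute one. Reordering therefore reduces the exposure but does not remove it.

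**The case against.** A reader might infer that the monitor rating is anchored to self-report and so is not a separate behavioural measure. The documents do not support that. They contain no data on anchoring. The order within a row rests on the sequence of sentences in a table cell, and the narrative has it reversed. Monitors also rate speech, movement and tremor, and at the end of the session "Monitors will also complete a questionnaire to rate the overall qualitative nature"; these are distinct from a drug-strength number. This objection stands in full and confines the point to a risk to the intensity score.

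It can also be said that the plan never calls the two measures independent or uses one to confirm the other, since it frames the analysis as one of subjective response. That is correct. What remains is that the plan lists them side by side for correlation with imaging and does not warn that they may overlap.

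A third objection is that scoring after the prompt can be defended, because how a volunteer answers is itself observable evidence of drug effect. That is a fair reason for choosing that order deliberately, but the plan does not give it.

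Finally, the magnitudes rest wholly on assumed inputs and the reordering is only a partial remedy. Both are true.

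**Conclusion.** The point holds in a limited form. Followed as listed, the schedule has monitors score intensity after hearing the volunteer's number; if the order within a row is open, it may differ between monitors or volunteers. In neither case does the plan protect the monitor intensity score, and its correlation with imaging may partly repeat the self-report correlation.

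The size is unknown. The rise from 0.30 to 0.39-0.52 depends on the assumed 0.5, 0.6 and 20% to 50%, and does not show that a brain finding will appear confirmed: at 20 participants the expected correlation passes the significance threshold only at the upper end of that range. What is affected is a set of secondary correlations between first-session ratings and second-session imaging. The primary placebo-versus-drug imaging contrast and the sample size are untouched. The change is worth making because it costs almost nothing and the problem cannot be undone after collection.

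**What to change.** 1. In every post-dose row of the first-session schedule, and in the session script, state that monitors record observed intensity, speech and movement before they prompt the volunteer for the verbal rating. Word the First experimental session day narrative so that it expressly gives the same order.
2. In Statistical analysis of behavioral data, add that the correlation between monitor intensity and self-rated strength will be reported, and that the two scores will be treated as overlapping measures, not as independent confirmation of each other. This is needed even after step 1, because monitors will remember earlier numbers. It can also be applied to any sessions already run in the listed order.

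Cost: no extra staff, equipment or data. The self-rating is delayed by a few seconds at each time point, and monitors score without having seen the response to the current prompt.

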Study Protocol with Statistical Analysis Plan

Study Title: Effects of Salvinatorin A on Brain Function

Clinical Trials ID (NCT number): NCT03418714

Last Protocol Approval Date: October 5, 2018

This protocol will include two or more administrations of an inhaled dose of salvinorin A in experimental laboratory settings. The first experimental session will involve administration of a 15 µg/kg dose of salvinorin A without brain fMRI scanning. The first session will allow the participant to become familiar with the inhalation procedure as well as the dose of salvinorin A that they will encounter in the fMRI scanner. If the volunteer displays involuntary movement or no memory for the experience, we may repeat the drug administration at a lower dose (12 µg/kg). The final experimental session will involve inhalation of either 12 or 15 µg/kg salvinorin A during fMRI scanning. Our previous research has shown that both 12 and 15 µg/kg doses of salvinorin A are well tolerated in participants with history of hallucinogen use (Johnson et al., 2011; Johnson, MacLean, Caspers, Prisinzano, & Griffiths, 2016; MacLean, Johnson, Reissig, Prisinzano, & Griffiths, 2013; Maqueda et al., 2015).

The primary objective of this study is to investigate the effects of salvinorin A on human brain activity and connectivity. Secondary objectives include investigating the relationship between individual differences in subjective effects of salvinorin A and individual differences in brain response to salvinorin A.

Study Procedures

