Second experimental session day: During the second experimental session day, participants will be lying down in a supine position within an MRI scanner during administrations of placebo (inhaled air) and a 15 or 12 µg/kg dose of salvinorin A (whichever dose did not yield erratic movement during the first experimental session). Participants will be told that they are being continuously monitored by an intercom and can stop the scan at any time, but that it is best for them to remain still and refrain from any head, face or jaw movements. Participants will also be told that a study team member will remain in the scanner room with them throughout the procedures. The placebo condition (inhaled air) will always precede the salvinorin A condition. MRI scans will be used to obtain structural brain images, as well as functional data that permit the direct measurement of oxygenated blood (using blood-oxygenation level dependent [BOLD] techniques) to assess acute effects of salvinorin A on brain function. Heart rate (via pulse oximetry), respiration, and end-tidal carbon dioxide may also be collected in order to correct for artifacts in BOLD signal. BOLD signal data will be collected during two 20 minute scans (one scan for placebo and one scan for salvinorin A). During each scan, an inhalation period will begin 30 seconds after the beginning of BOLD data collection, and will be cued via audio stimulus using MR-safe headphones. A study team member will be present in the scanner room with the volunteer during scanning and inhalation procedures, to provide support to the participant during procedures. Participants will be told that one of the inhalations will be the dose of salvinorin A that they received during the first session, and the other inhalation will be either a placebo or a variable dose of salvinorin A, but no dose of salvinorin A higher than the dose they received during the first session will be administered.

All imaging procedures will be performed using 3T Siemens MRI scanner at the MRI Research Service Center at Johns Hopkins Hospital, by individuals specifically trained in these procedures. MRI assessments

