involve standard methods and established pulse sequences utilized in research evaluations and do not involve the injection of any contrast or other invasive procedures. We will work closely with the neuroimaging experts in the MRI Research Service Center to ensure safe and effective implementation of the tasks conducted in the scanner. [name], the principle investigator on the team, has extensive experience with brain imaging and is currently leading MRI and PET neuroimaging studies of the acute effects of the classic hallucinogen psilocybin. [name] will oversee the development and conduct of brain imaging procedures and analysis of the resulting data.

After completing the scanning procedures, the participant will complete brief (e.g., 10-15 minute) behavioral measures and/or questionnaires regarding the subjective effects that they experienced during the scanning session. These measures will be used along with ratings made in the scanner to interpret differences in brain activation between participants and across conditions. For example, changes in brain activation may be correlated with ratings of subjective effects (e.g. the Mystical Experience Questionnaire, or the Challenging Experience Questionnaire) experienced during the scanning procedures. Subjects will also be asked to write a narrative description of the experience of each salvinorin A session within about one week after a session.

Participants will undergo drug administration during collection of BOLD signal in the MRI. Real-time fMRI analysis techniques may be employed to monitor volunteer head motion as the scans are collected. If participants exhibit gross (> 1mm of movement in any plane) frequent (for more than 25% of the scan time) head motion, we may repeat the given drug administration and scan, since frequent gross motion may invalidate BOLD imaging data (Power, Barnes, Snyder, Schlaggar, & Petersen, 2012; Power et al., 2014). We may repeat drug administration and scanning up to two times. No more than one salvinorin A administration will occur on a single day. Repeated administrations of salvinorin A may occur on consecutive days.

Schedule of Events for Second Experimental Session Day

Time Point (minutes from drug administration)	Procedure	Description
-65 (or more)	Intake procedures	Participant will complete drug and pregnancy urine tests, and complete a pre-session questionnaire to assess the psychological “set” of the volunteer (including mood state and cognitive state)

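### The protocol both rules out and permits two salvinorin A doses in one day, so the air scan that anchors the primary contrast may follow an active dose in some participants

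*Combined protocol and SAP*

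**What the plan says.** **Same-day dosing.** Under Second experimental session day, after the text on repeat scans for head motion, the protocol states: "No more than one salvinorin A administration will occur on a single day". It adds that repeats may fall on consecutive days. The section on study duration and number of visits, however, permits the first and second drug sessions to be held within one day. The Illustrative Timeline says the same of Visits 3 and 4. Both visits include a salvinorin A inhalation.

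**The reference scan.** Study Statistics defines the primary outcome as change during the acute drug effect, "compared to the preceding period after inhalation of the placebo condition (inhaled air". There is one 20-minute scan per condition, and "The placebo condition (inhaled air) will always precede the salvinorin A condition". The Schedule of Events for the second session day fixes that sequence.

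**Repeats.** After gross, frequent head motion, "we may repeat the given drug administration and scan, since frequent gross motion may invalidate BOLD imaging data". The sentence does not say whether a repeated drug scan gets a new air scan.

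**Analysis.** The objective is causal in wording: "The primary objective of this study is to investigate the effects of salvinorin A on human brain activity and connectivity". Under MRI data analyses, the plan names standard preprocessing and says that regional time courses "will be extracted and submitted to functional connectivity analysis". It does not mention scan order, same-day dosing or which scans form a pair.

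**The concern.** The primary contrast is only as clean as its air scan. If some participants inhale salvinorin A earlier on the scan day and others do not, the air condition is not the same for everyone, and the plan neither records nor handles the difference. Any residue of the earlier dose would move the reference, and therefore the estimated drug effect, by an unknown amount in an unknown subset.

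The fixed order is a separate and lesser matter. Scan number and condition are the same variable, so time in the scanner, drift, or anticipation after an uneventful first inhalation is added to the drug effect. A reader of the results should be told so.

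**Working it through.** **1. Same-day text side by side.**
- Second experimental session day: at most one salvinorin A administration per day, stated without exception.
- Study duration section and Illustrative Timeline: Visit 3 (drug) and Visit 4 (air, then drug) may share a day, which means two administrations.

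Both cannot hold as written.

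**2. How close the earlier dose could be.** The first session's schedule runs to 45 minutes after inhalation. The second session's intake begins at least 65 minutes before its drug inhalation, and the air scan starts 20 minutes before it, so intake to air scan is at least 65 − 20 = 45 minutes. Run back to back, the schedules put the air scan about 45 + 45 = 90 minutes or more after the first dose. Both are labelled approximate. The protocol reports that subjective effects resolved within 45 minutes in earlier work, but gives no figure for brain measures.

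**3. Size of a shift in some participants.** The plan gives no figure, so the following are assumptions: one outcome, n = 20, two-sided 5% paired test, no drug effect, and a shift of 0.5 SD of the paired difference in k participants. The mean moves by 0.5k/20.

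| k | mean shift (SD) | simulated false positives |
|---|---|---|
| 2 | 0.05 | 5% |
| 4 | 0.10 | 7% |
| 6 | 0.15 | 9% |

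The same table applies if k participants have a repeated drug scan compared with an air scan from another day.

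**4. Fixed order.** With columns for intercept, drug and second scan, the design matrix has rank 2 of 3. The expected contrast is drug effect + (scan 2 − scan 1 change), and no order term could be fitted. For an assumed shift s in SDs of the paired difference, the rejection probability comes from the noncentral t with 19 df and noncentrality s√20. Relative bias is s divided by the true effect.

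| s | false positives, no drug effect | bias if true effect 0.89 | bias if true effect 4 |
|---|---|---|---|
| 0.2 | 13.6% | 22% | 5% |
| 0.3 | 24.7% | 34% | 7.5% |
| 0.5 | 56% | 56% | 12.5% |

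The 0.89 is the plan's psilocybin rating effect. The 4 is its lower bound for the salvinorin A rating effect (eta-squared 0.81; 2√(0.81/0.19) = 4.1). Neither is an imaging effect. Using 0.89 as a paired effect is my assumption: a paired test at 0.89 reaches 80% power with 12 participants, whereas the plan quotes 21 from a cited source, so its scale is unresolved.

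**5. Can existing data separate order from drug?** Each scan has little pre-drug signal: "During each scan, an inhalation period will begin 30 seconds after the beginning of BOLD data collection", or 30/1200 = 2.5% of the scan. The alternative is an early-minus-late difference in the drug scan minus the same difference in the air scan. With two equal windows whose noise correlates r, its SD is √(4(1−r)/(1+r)), which is 2.00 at r = 0 and 1.15 at r = 0.5. The 95% half-width, 2.093 × SD/√20, is 0.94 or 0.54 SD, against 0.47 SD for the primary contrast. If the drug effect lasts through the scan, power is about 5%. Anticipation tied to the second inhalation is not removed.

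**The case against.** **On the same-day text.** The one-per-day sentence stands in a paragraph about repeat scans and might be meant for repeats only. It is not worded that way, and the narrower reading would not help the reference scan: same-day sessions would then simply be allowed, and the air scan could still follow an active dose. A reader might go further and infer that the air scan is contaminated. The documents do not support that. They do not say that any participant had both sessions in one day, and their own timings place the air scan well after subjective effects had resolved in earlier studies. What stands is that the reference condition may differ between participants.

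**On repeats.** A reader might infer that repeated drug scans will lack an air scan. The fixed sequence, and the timeline's reference to repeating a test session, point the other way. This is an ambiguity, not an established flaw.

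**On order.** The order is disclosed, and placing air first avoids carry-over from the scanner dose. No order effect is evidenced, and the false-positive figures require both an assumed shift and no drug effect. There are partial mitigations: the first session familiarises participants with the procedure, structural scanning precedes the air scan, heart rate, respiration and end-tidal carbon dioxide may be recorded, and participants are told that "the other inhalation will be either a placebo or a variable dose of salvinorin A". The planned correlations with subjective response also help, since a shift common to everyone cannot create them. All this is fair and makes the order point minor. None of it removes the confound from the mean contrast.

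**Conclusion.** The contradiction on same-day dosing is plain on the page and should be resolved, because it decides whether the primary reference scan means the same thing for every participant. Its effect on the result is unknown. Under the assumptions above it is small if few participants are affected (false positives of 5% to 9%) and grows with their number.

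The order point holds as a limit on interpretation only. A reader might infer that the study cannot show a drug effect, or that the order bias is large. The documents give no size or direction for a first-to-second-scan change, and against an effect as large as the salvinorin A rating effect a shift of 0.2 to 0.5 SD would be minor. Equally, the plan has no imaging data from which to assume that the brain effect is that large.

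**What to change.** 1. Reconcile the one-administration-per-day sentence with the study-duration section and the Illustrative Timeline. Which rule applies is for the investigators.
2. If same-day sessions remain possible, record them for each participant and repeat the primary contrast without those participants.
3. State in the analysis plan that the primary contrast uses air and drug scans from the same session, so that any repeated drug scan is compared with an air scan from that session. The fixed sequence already implies this.
4. Keep the fixed order. Add a sentence that the mean contrast estimates the drug effect plus any change from first to second scan, and word the conclusion to match. This separates nothing, but it tells readers what was estimated.

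I would not require the early-minus-late comparison, given its imprecision.

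The cost is protocol and SAP wording, one recorded item, one rerun of the contrast, and at most one 20-minute air scan per repeated session.
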